Leveraging the Depression And Primary-care Partnership for Effectiveness-implementation Research (DAPPER) – will be initially randomized to 12 weekly one-hour sessions of IPT (3 months) or 6 months of fluoxetine (tapering up to 60mg). Those participants who are not in remission with at the conclusion of initial treatment will be re-randomized to second-line treatment (see below). Prior to randomization, participants will be given the option to receive their treatment at the health facility or by telephone.

Participants who are randomized to fluoxetine and conduct their visits by telephone will need to collect their medication at the health facility. If participants do not collect their medication at the health facility, fluoxetine may be delivered to participants in the community. A smaller, Part 2, of the study will consist of qualitative interviews and focus groups to assess the overall implementation strategy and gather feedback on the specific interventions. Please see "Part 2," below (and additional consent for this aspect of the study, attached).

Randomization and blinding: Randomization will take place after baseline measures are complete. Randomization will be done in blocks of 10 and stratified by sex and telephone vs in-person treatment to ensure that the treatment groups are approximately equal in size and in gender distribution and telephone vs in-person treatment. See below

for second randomization information. Clinical evaluators who conduct follow-up assessments will be blinded to treatment assignment. Participants, IPT therapists, fluoxetine providers cannot be blinded because they will either be providing or receiving the IPT and/or Fluoxetine treatment and therefore they will know their treatment status. In addition, at least one study coordinator will not be blinded to assist with tracking of participants.

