Study visits: To characterize the trajectory of symptom change during treatment, participants will be re-evaluated at the mid-point of treatment (month 1.5 for IPT and month 3 for fluoxetine). Treatment mid-point data is valuable because it can inform the minimum duration of treatment necessary to optimize mental health gains in a setting of scarce mental health resources. For example, if 90% of all observed treatment gains are achieved in the first half of treatment, subsequent implementation efforts might consider shortened courses of treatment. Participants will be assessed at month 3 (end of IPT treatment, mid-point of fluoxetine treatment) and at month 6 (end of fluoxetine treatment). For those participants who are in remission from depression and/or PTSD, follow up assessments will then continue at 9 month, 12 month and then at six month intervals until month 30 to assess for maintenance of gains and relapse. Assessments may be done at the health facility or by telephone. We are defining remission as absence of disease as defined by threshold criteria for Diagnostic and Statistical Manual of Mental Disorders-V (DSM-V) for PTSD and MDD. Those participants who have not yet remitted will be re-randomized to: switch of treatment (from IPT to fluoxetine or vice versa) or combination treatment (addition of IPT to fluoxetine or vice versa). See Figure 3.

Assessment schedule and rationale:

In order to characterize the trajectory of symptom change during treatment, participants will be re-evaluated at the mid-point of treatment (month 1.5 for IPT and month 3 for fluoxetine). Treatment mid-point data is valuable because it can inform the minimum duration of treatment necessary to optimize mental health gains in a setting of scarce mental health resources. For example, if 90% of all observed treatment gains are achieved by month 1.5, subsequent implementation efforts might consider shortened courses of treatment. Participants will be assessed at end of treatment (month 3 for IPT and month 6 for fluoxetine) and fluoxetine recipients will be tapered off the medication. At six months, participants will be re-assessed and then monitored at 6-month intervals until month 30 (Figure 3). Assessment visits may be done at the health facility or over the telephone.

Measures (Table 1): *Demographics.* We will obtain usual demographic measures, education, including individual income, assets, education and school fees, healthcare utilization, and time allocation.

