therapist (see therapist selection and training procedures, above), in 12 weekly 60-minute sessions. Participants randomized to receive fluoxetine will meet or speak with fluoxetine trained provider at baseline, 2 weeks, 4 weeks, 2, 3, 4, 5, and 6 months, for a total of eight appointments. Participants will be assessed for initiation of fluoxetine and advisement on common side effects. Fluoxetine participants will be started on 20mg (1 capsule per day) and will return for assessment of initial efficacy/tolerability at week 2. If the participant does not have any prohibitive side effects, dose will be maintained at 20mg (1 capsule). Participant will return for re-assessment at week 4, if the participant does not have any prohibitive side effects and does not have improvement on the Patient Health Questionnaire-2 (PHQ-2), dose will be increased to 40mg (2 capsule). At month 2, if the participant does not have any prohibitive side effects and does not have improvement on the PHQ-2, the dose will be increased to 60mg (3 capsule). Participants receiving treatment by telephone may be able to receive a 3 month supply at the minimum dose (20 mg per day). If the dose is increased during the intervening treatment visits, the participant will need to receive additional medication. Participants receiving treatment by telephone will be asked to pick up their medication within two days of their treatment call. If they do not collect their medication within 2 days, the medication will be delivered in the community. Studies support that higher fluoxetine doses do not show additional benefit.(Jakubovski, Varigonda, Freemantle, Taylor, & Bloch, 2016) See Protection of Human Subjects section for details on fluoxetine side effect management. The participant will be maintained at 20, 40 or 60 mg at the month 3, 4, and 5 visits, if the participant does not have any prohibitive side effects. At the month 6 visit, participants will be given instructions for tapering off fluoxetine, with decrease of the dose by 20mg

increments each week until reaching zero. Participants who were maintained on 20 mgs throughout the treatment period will have fluoxetine discontinued at the end of 6 months. IPT therapists and fluoxetine-trained providers will be compensated per IPT/medication session/day completed, at the local currency equivalent of 10usd.

Fluoxetine treatment duration: Participants treated with fluoxetine will be tapered off fluoxetine at month 6.

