Retention: Based on previous work, retention is not expected to be a problem. Our pilot study of IPT for Sudanese refugees in Cairo had a 93% retention rate; our study of IPT for survivors of the Sichuan earthquake had an 85% retention rate and our ongoing study of integrated IPT care with HIV+GBV+ women in Kisumu has 300 enrollees with 20 dropouts (93% retention, to date). However, given uncertainty regarding generalizability to the KCH and other Kisumu County Ministry of Health facilities adult primary care clinics, the more conservative estimate of 20% drop-out will be used. However, provision of treatment over the telephone may improve retention rates. As part of retention efforts, participants will be asked to provide the name and phone number of a trusted adult who can be contacted if the study has concerns about participants' welfare or whereabouts. Therapists and fluoxetine providers will be asked to provide study cell phone numbers to study participants. Missed appointments will be followed with at least two efforts to reach the participant directly and/or through their contact (80% cell phone coverage). Likewise, at least two efforts will be made to reach drop-out participants for remaining measures.

Acute mental health care: IPT therapist and fluoxetine training will include risk assessment and referral procedures for acute mental health care needs. See Protection of Human Subjects section for details.

Clinical evaluators: Clinical evaluators will be blind to treatment group and will conduct baseline screening at the primary care clinic prior to initiating treatment, as well as re-assessments at months 1.5 (mid-treatment for IPT), 3 (mid-treatment for fluoxetine), 6, 9 month 12, 18, 24 and 30. Candidate clinical evaluators will undergo a two day training during which they will be introduced to the study measures and their proper application. At the conclusion of the training, the candidates will be observed in their administration of the measures, assessing for accuracy and completeness. If successful, they will be evaluated for reliability by conducting a group interview and comparing measure results. Those who demonstrate both accuracy and inter-rater reliability will be invited to join the study. Monetary compensation will be provided for completed measures at the local currency equivalent of 7usd.

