Data collection. Data collection will use tablets programmed with Research Electronic Data Capture (REDCap), similar to the electronic data system that we are currently using in Kisumu, Kenya (Online Data Kit [ODK]). REDCap now has an offline feature which does not require internet connectivity for data entry and can be later connected to the internet for upload to secure server.

Effectiveness outcomes

Clinical evaluators. Clinical evaluators will consent and screen study participants, complete baseline measures and then refer participants to (un-blinded) study coordinators for randomization. Blinded to group assignment, clinical evaluators will conduct 1.5 month (IPT treatment mid-point), 3 month (IPT end-of-treatment, fluoxetine-mid-treatment), and follow-up assessments. Candidate clinical evaluators will undergo a two day training during which they will be introduced to the study measures and their proper application. At the conclusion of the training, the candidates will be observed in their administration of the measures, assessing for accuracy and completeness. If successful, they will be evaluated for reliability by conducting a group interview and comparing measure results. Those who demonstrate both accuracy and inter-rater reliability will be invited to join the study. Monetary compensation will be provided for completed measures at the local currency equivalent of 7usd.

Data analysis plan

For *Hypothesis 1a* the analysis is standard intention to treat for 3 month (end of treatment) data. Our basic analysis strategy will be to fit logistic regression models for the outcome of MDD and/or PTSD remission, in this case with the predictor of group assignment (IPT or fluoxetine), demographics and severity of baseline depression and/or PTSD symptoms (BDI and PCL) . *Hypothesis 1b* will be analyzed for the sub-group of participants who are in remission from MDD and/or PTSD at months 1.5 or 1.5 and 3 and will use weighted generalized estimating equations logistic regression to accommodate the repeated measures on this subgroup through month 30.

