Acceptability and Appropriateness. Interview material will be recorded in audio files, transcribed and translated. Dedoose software will be used to analyze the resulting text using grounded theory. Grounded theory sorts data in three ways: through concepts, categories and propositions. Concepts are identified by seeking conceptual similarities among focus groups/interviews. These concepts are grouped to develop categories of concepts. Categories are then compared and grouped to develop propositions or theoretical constructs about the phenomena of interest. Dedoose software facilitates coding of observations to work toward the theoretical construct. Data will be collected using a “triangulation” technique that compares information from various sources (focus groups, individual interviews) in order to increase the reliability and validity of the findings. ***Feasibility and Fidelity.*** Feasibility and fidelity measures will be assessed by sample means and proportions, with 95% confidence intervals, and compared to pre-specified benchmarks (above).

Service delivery mechanism: availability and affordability. *Hypothesis 1c* will be addressed by calculating RE-AIM for IPT and fluoxetine according to the procedures outlined in Glasgow et al.(Glasgow, Vogt, & Boles, 1999) Then, we will then evaluate how RE-AIM scores correlate with availability and affordability measures (Table 2) for IPT versus fluoxetine. Finally, we will evaluate for mediation by treatment completion. Specifically, we will begin with logistical regression models of RE-AIM score including availability factors and affordability factors. If any significant relationships exist, we will construct figures of hypothetical relationships between variables that are significantly associated with RE-AIM score and create path diagrams, using effect sizes to identify potential causal pathways between availability, affordability and RE-AIM scores for IPT versus fluoxetine.

Table 2: Calculating RE-AIM from an Effectiveness-Implementation Hybrid Type I (SMART-DAPPER)(Farris, Will, Khavjou, & Finkelstein, 2007; Glasgow, Klesges, Dzewaltowski, Estabrooks, & Vogt, 2006)

1	Reach will be calculated as the ratio of study participants who are eligible for SMART-DAPPER compared with those who choose to participate. Reach is the first assessment of RE-AIM.
Effectiveness Outcomes	
2a	MDD and/or PTSD remission from IPT or fluoxetine at month 3 (IPT) and month 6 (fluoxetine).

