2b	MDD and/or PTSD remission at month 1.5 (treatment mid-point) for IPT and at 3 months (treatment mid-point) for fluoxetine to identify the proportion of treatment gain achieved at mid-point compared with end of treatment (month 3). Treatment Effectiveness is a key aspect of RE-AIM.
3	Maintenance of month-3 remissions from IPT or and month 6 remissions from fluoxetine at follow-up assessments (months 6 (for IPT), 9, 12, 18, 24 and 30). Maintenance of gains is an individual level measure of Maintenance in RE-AIM.
Implementation Outcomes	
4	Both IPT and fluoxetine will be acceptable treatments for delivery in primary care as determined by qualitative interviews.
5	Both IPT and fluoxetine will be appropriate treatments for delivery in primary care as determined by qualitative interviews.

- 6 Both IPT and fluoxetine will be feasible treatments as determined by completion rates. *With the exception of those who leave the study because their symptoms remit, completion rate will be used as an individual level measure of Adoption in RE-AIM.*
- 7 Both IPT and fluoxetine will have strong treatment fidelity as determined by protocol adherence to IPT and fluoxetine administration. *Fidelity is a key component of Implementation in RE-AIM.*

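### Hypothesis 1a is analysed on month-3 data labelled end of treatment for both arms, although month 3 is mid-treatment for fluoxetine; its similarity claim also has no margin

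*Protocol*

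**What the plan says.** **Hypothesis.** Protocol, Hypothesis and Specific Aims: Hypothesis 1a expects the two initial treatments to have similar efficacy for remission after treatment.

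**Analysis time.** Protocol, Data analysis plan: for this hypothesis "the analysis is standard intention to treat for 3 month (end of treatment) data", by logistic regression on group assignment, demographics and baseline severity. No month is given separately by arm.

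**What month 3 is.** The clinical-evaluator paragraph just before that plan lists "3 month (IPT end-of-treatment, fluoxetine-mid-treatment), and follow-up assessments". The Clinical evaluators paragraph that follows Acute mental health care also lists "3 (mid-treatment for fluoxetine), 6, 9 month 12, 18, 24 and 30".

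**When treatment ends.** Study Procedures: "12 weekly one-hour sessions of IPT (3 months) or 6 months of fluoxetine". Assessment schedule and rationale: "Participants will be assessed at end of treatment (month 3 for IPT and month 6 for fluoxetine". Fluoxetine treatment duration: "Participants treated with fluoxetine will be tapered off fluoxetine at month 6". Table 2, row 2a: "MDD and/or PTSD remission from IPT or fluoxetine at month 3 (IPT) and month 6 (fluoxetine". Row 2b, however, reads "at 3 months (treatment mid-point) for fluoxetine to identify the proportion of treatment gain achieved at mid-point compared with end of treatment (month 3".

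**SAP.** It models change in risk from baseline to the end of first-line treatment, with the time-by-group interaction as the primary test. It reports ratios of relative risks with confidence intervals. It prints no month, confidence level or margin, and it carries the same date as the protocol.

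**The concern.** The Data analysis plan is the only place that ties a visit to Hypothesis 1a by name, and its label is wrong for one of the two randomised arms. An analyst who followed it would take the month-3 fluoxetine visit. One who followed the SAP would most naturally take month 6. These are different contrasts with different limitations, and a plan should not leave that choice to be made once data are in hand.

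The second issue is inferential. A test of difference that fails to reject does not show similarity. Without a margin, a non-significant interaction could be reported as support for Hypothesis 1a when it is only inconclusive.

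**Working it through.** **Time point: the texts side by side**

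- Month 3 for IPT: 3 of 3 months complete, so it is the end of treatment.
- Month 3 for fluoxetine: 3 of 6 months complete, so it is the mid-point. Two clinical-evaluator paragraphs say so directly.
- Study Procedures, the assessment schedule, the fluoxetine duration paragraph and Table 2 row 2a all put the fluoxetine end at month 6.
- Table 2 row 2b cannot be right for fluoxetine, because it places both the mid-point and the end of treatment at month 3.
- Study Procedures re-randomises non-remitters when initial treatment concludes. By month 6, IPT non-remitters may therefore be on second-line treatment, and a common month 6 is not a clean first-line comparison.

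**Similarity: what a test of difference could show**

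The plan has no sample-size figure for Hypothesis 1a. Its total is built on switch versus combination: 242 × 4 = 968; 968 / 0.5 = 1,936; 1,936 × 1.4 = 2,710. That reproduces the stated total but supplies no margin for Hypothesis 1a.

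Inputs and assumptions:

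- Equal arms: 2,710 / 2 = 1,355.
- Loss of 0% to 20% by the end of first-line treatment. Retention plans on 20%, and the Feasibility benchmark is under 20% leaving during treatment. At 20%, n = 1,355 × 0.8 = 1,084. The 40% in the sample size section covers 33 months, so it is not used here.
- Remission p from 0.38 (Background) to 0.67 (Sample size calculations says over two-thirds), with 0.50 between.
- Unadjusted risk difference, normal approximation, two-sided 5% test.
- Margins m are illustrative; the documents give none.

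Formulas, in percentage points:

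- SE = 100 × √(2p(1−p)/n)
- P(non-significant | true difference 5) = 1 − [Φ(5/SE − 1.96) + Φ(−5/SE − 1.96)]
- Equivalence power at no true difference = 2Φ(m/SE − c) − 1, with c = 1.96 if a 95% interval must lie inside ±m, and c = 1.645 for two one-sided 5% tests

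Example, p = 0.50 and n = 1,355: SE = 100 × √(0.5/1,355) = 1.92. Then 5/1.92 − 1.96 = 0.64 and Φ = 0.740, so the chance of non-significance is 0.260.

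| p | n per arm | SE | Non-significant at true 5 points | Power ±5, 95% interval | Power ±5, two 5% tests |
|---|---|---|---|---|---|
| 0.38 | 1,355 | 1.87 | 0.235 | 0.529 | 0.700 |
| 0.38 | 1,084 | 2.09 | 0.331 | 0.339 | 0.549 |
| 0.50 | 1,355 | 1.92 | 0.260 | 0.480 | 0.662 |
| 0.50 | 1,084 | 2.15 | 0.356 | 0.287 | 0.505 |
| 0.67 | 1,355 | 1.81 | 0.210 | 0.581 | 0.738 |
| 0.67 | 1,084 | 2.02 | 0.303 | 0.394 | 0.594 |

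At ±7.5 points, power is 0.875 to 0.972 with the 95% interval and 0.935 to 0.988 with two 5% tests. At ±10 points it is at least 0.993 under either rule.

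**The case against.** The best reply is that the intended time point is already clear. Hypothesis 1a speaks of remission after treatment. The assessment schedule and Table 2 row 2a split the months by arm, and the SAP uses the end of first-line treatment, the same point at which it re-randomises. The SAP also replaces the protocol's model (log-binomial GEE instead of covariate-adjusted logistic regression), so few analysts would run the protocol sentence as printed. Most of this stands. It means the time point should be corrected rather than treated as an open choice. It does not remove the error: the two documents share a date, neither says which prevails, and the SAP prints no month.

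A reader might go further and infer that the trial's main comparison is biased against fluoxetine. The documents do not support that. They give no month 3 to month 6 change in remission for this trial. The one related remark, from another fluoxetine study and on PHQ-9 scores, reports most of the gain by weeks 6 to 12 and little afterwards. That hints at a modest shift but does not settle it for remission here.

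On similarity, it is fair to say that the SAP nowhere claims a non-significant interaction proves similarity, and that it reports intervals. This is why the point ranks below the time-point error. A reader might also infer that the trial is too small to show similarity. The figures do not bear that out unless the margin is near 5 points, and even there the answer depends on the decision rule.

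**Conclusion.** The time-point statement is wrong as written and must be corrected. This rests on the text alone, needs no numerical assumption, and carries no claim about the size or direction of bias. The slip in Table 2 row 2b is smaller and of the same kind.

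The missing margin is a should-fix gap in inference. With 1,084 to 1,355 per arm and 38% to 67% remission, a true 5-point difference would be missed 21% to 36% of the time, so non-significance would not support Hypothesis 1a. Equivalence power at an assumed 5-point margin is 29% to 58% with a 95% interval, or about 51% to 74% with two one-sided 5% tests. It is 87% or more at 7.5 points and 99% or more at 10 points under either rule. These figures are on the risk-difference scale; the SAP reports ratios of relative risks, so they do not carry over directly.

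**What to change.** **Must fix.** Amend the Data analysis plan and Table 2 row 2b to agree with Hypothesis 1a, the assessment schedule, Table 2 row 2a and the SAP. Hypothesis 1a then uses the end-of-first-line-treatment assessment in each arm: month 3 for IPT, month 6 for fluoxetine. Print those months in the SAP. State as a limitation that the arms are then compared at different times since randomisation. A month-3 comparison of both arms is optional; if run, label it secondary and note that fluoxetine is half complete. If a common month 6 is shown, say that it includes second-line treatment of IPT non-remitters.

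**Should fix.** Either reword Hypothesis 1a as a test of difference, or state a justified margin, on the scale to be reported, together with the confidence level, and judge the interval against it. The SAP is written in the past tense, so a margin set after outcomes were known should be labelled post hoc.

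**Cost.** Wording in two documents and, if wanted, one extra model on visits already scheduled. A margin carries the risk that a tight one is not met and the result must be called inconclusive. Rewording avoids that but gives up the similarity claim.

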Objectives: We propose to partner with local and national mental health stakeholders in Kenya to evaluate: (1) non-specialist delivery of evidence-based depression and/or PTSD treatment integrated within existing healthcare centers and by telephone in regard to clinical effectiveness and implementation parameters; including (2) costs and cost-benefit ratios for depression and/or PTSD care. Given that evidence-based psychotherapy and second-generation antidepressants are the two leading first-line treatments for depression and/or PTSD and are feasible to deliver in Kenya, our goal is to test an implementation strategy for improving equitable access to these treatments by integrating them with primary care.

Methodology:

Given the novelty of non-specialist depression care and primary care integration for Kenya, we will use an effectiveness-implementation hybrid design type I, which emphasizes effectiveness outcomes for the new setting and study population, while also gathering implementation data for future scale up. In collaboration with the 80-member FACES team currently providing integrated HIV care to Kisumu County Hospital (KCH) primary care outpatient clinics (~10,000 patients/month), we will randomize 2000 adult KCH and other Kisumu County Ministry of Health primary care patients with Major Depressive Disorder (MDD) to receive IPT delivered in person or by telephone by non-specialists trained in the study or fluoxetine delivered by fluoxetine trained providers in the study and follow them for 30 months. We will use the Exploration, Preparation, Implementation and Sustainment (EPIS) framework to inform the research and incorporate positive findings into practice. Given the high prevalence of MDD-PTSD co- morbidity, we will leverage the R01 to support a Sequential, Multiple Assignment Randomized Trial (SMART) by recruiting an additional 710 participants with MDD and/or PTSD (irrespective of HIV status) for a

total of 2710 participants. Local non-specialists will be trained in mental health care for the SMART and hired through the Kenyan Ministry of Health to work at KCH and other Kisumu County Ministry of Health facilities. After the study, Kisumu County will continue their payroll and the fluoxetine supply.

Data analysis: the study will compare short and long term (relapse) outcomes for IPT versus fluoxetine treatment (Aim 1), and calculate costs and cost-benefit ratios for each treatment arm (Aim 2).

Results:

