Hypothesis 1b: Participants who remit with IPT or combination treatment will have fewer relapses over follow-up than those who remit with fluoxetine.

Aim 2:

Investigate key presumed mediators of the relationship between treatment and remission

Hypothesis 2a: For initial treatment with IPT, change in social support will mediate the relationship between treatment and remission—improved social support will be associated with remission

Hypothesis 2b: For initial treatment with fluoxetine, change in emotional reactivity will mediate the relationship between treatment and remission—decreased emotional reactivity will be associated with remission.

Aim 3: Identify demographic and clinical moderators of the relationship between treatment and remission.

Hypothesis 3a: Time or cost for transport between participants' residences and KCH, and other Kisumu County Ministry of Health facilities will moderate the relationship between treatment and remission—higher time/cost will decrease the effect of initial treatment with IPT relative to fluoxetine (more treatment visits required for IPT versus fluoxetine treatment).

Hypothesis 3b: Severity of MDD and/or PTSD symptoms among non-remitters will moderate the relationship between subsequent treatment and remission, such that higher severity will decrease the effect of treatment on remission for treatment switch relative to treatment combination.

Hypothesis 3c: Q learning will produce personalized treatment algorithms using the above or other moderators.

Aim 4. Estimate the costs and cost-benefit ratios for fluoxetine and IPT treatment of depression and PTSD.

Hypothesis 4a: Pooled cost-benefit ratios will show that depression and/or PTSD treatment leads to net economic gain for individuals and households at month 6;

Hypothesis 4b: Separate analyses will find that IPT has a more favorable cost-benefit than fluoxetine at month 30.

Aim 5. Determine the acceptability and feasibility of delivering SMART-DAPPER treatments by telephone.

Hypothesis 5a. Telephone IPT will be acceptable and feasible.

Hypothesis 5b. Telephone fluoxetine provider appointments will be acceptable and feasible.

Aim 6. Determine the effect of telephone treatment delivery on retention in care.

Hypothesis 6a. Participants who elect to receive telephone treatment will have higher retention in care than those who receive face-to-face care.

Significance

The results of the proposed research will be significant in two ways:

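### As printed, the Hypothesis 1b relapse set closes at month 3, so no fluoxetine remission first seen at month 6 and no remission on combination can qualify

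*Protocol*

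**What the plan says.** Hypothesis 1b (Protocol, Hypothesis and Specific Aims) reads: "Participants who remit with IPT or combination treatment will have fewer relapses over follow-up than those who remit with fluoxetine". The Data analysis plan limits its analysis to participants "who are in remission from MDD and/or PTSD at months 1.5 or 1.5 and 3" and fits a weighted GEE logistic model to their repeated measures up to month 30. It does not say when relapse follow-up begins.

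The calendar comes from other sections. Under Study visits: "Participants will be assessed at month 3 (end of IPT treatment, mid-point of fluoxetine treatment) and at month 6 (end of fluoxetine treatment"). Under Study Procedures, those "who are not in remission with at the conclusion of initial treatment will be re-randomized to second-line treatment"; the second-line options are switch or combination, and the SAP describes the same re-randomisation.

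Other places describe relapse differently:

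- Table 2, row 3, a RE-AIM maintenance measure not labelled as Hypothesis 1b, uses "Maintenance of month-3 remissions from IPT or and month 6 remissions from fluoxetine at follow-up assessments". It does not mention combination.
- The Abstract says "the study will compare short and long term (relapse) outcomes for IPT versus fluoxetine treatment (Aim 1"), again without combination.
- Sample size calculations mentions relapse risk only for those who remit on initial treatment.
- The SAP covers change from baseline to the end of first-line treatment and the re-randomised comparisons. It contains no relapse analysis.

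**The concern.** Relapse is one of the two hypotheses under Aim 1, and the Data analysis plan gives the only analysis set tied to it. That set is fixed by visits no later than month 3, while the hypothesis concerns remissions that can occur later: on fluoxetine up to month 6, and on combination only after first-line treatment has failed. If the rule is followed, the combination part of the hypothesis cannot be tested. Fluoxetine remitters are also defined at mid-treatment or earlier, while IPT remitters may be defined at the end of treatment. The SAP does not resolve this.

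**Working it through.** There is no sample size or power figure for Hypothesis 1b to reproduce. The check is one of timing and set membership.

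**Inputs.** First-line IPT ends at month 3 and first-line fluoxetine at month 6 (Study visits). Combination is open only to non-remitters at the end of first-line treatment (Study Procedures, Study visits, SAP). Its earliest start is therefore month 3 after IPT and month 6 after fluoxetine.

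**Readings.** Write remission status as (month 1.5, month 3, month 6), with 1 for remission. Four readings keep the printed months:

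| Reading | Patterns that qualify | Latest qualifying visit |
|---|---|---|
| Literal: 1.5, or both 1.5 and 3 (equivalent to 1.5) | 100, 101, 110, 111 | month 1.5 |
| 1.5 or 3 | 010, 011, 100, 101, 110, 111 | month 3 |
| Both 1.5 and 3 | 110, 111 | month 3 |
| 3 only | 010, 011, 110, 111 | month 3 |

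**Results on all four readings.**

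- Pattern 001 never qualifies, so a fluoxetine remission first seen at month 6 is left out.
- The latest qualifying visit (month 3) is no later than the earliest start of combination (month 3), so no remission on combination can bring anyone in.
- Pattern 110 always qualifies. A fluoxetine participant who loses remission by month 6 stays in the set although then due for re-randomisation.

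**Results on some readings.** The literal and both-visits readings require remission at month 1.5, so they also drop patterns 010 and 011. These are remissions first seen at month 3, which is the end of IPT.

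It is unclear whether fluoxetine participants are assessed at month 1.5. Study visits says "participants will be re-evaluated at the mid-point of treatment (month 1.5 for IPT and month 3 for fluoxetine"), and Clinical evaluators lists "re-assessments at months 1.5 (mid-treatment for IPT), 3 (mid-treatment for fluoxetine), 6, 9 month 12, 18, 24 and 30". The economic surveys list month 1.5 with no limit by arm. If fluoxetine participants are not assessed then, the literal and both-visits sets contain no fluoxetine remitters at all.

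**Scale.** Sample size calculations plans 242 per second-stage arm, so 2 × 242 = 484 are assigned to combination. These are people assigned, not remitters. The first-line plan gives 968 / 0.50 = 1936 before drop-out inflation, hence 1936 − 968 = 968 first-line remitters, or 968 / 2 = 484 on fluoxetine if the 50% applies equally to both arms. The number first remitting at month 6 could be anything from 0 to 484. No remission rate by visit, or on combination, is given.

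**Follow-up if the set is anchored at the end of first-line treatment.** IPT: 30 − 3 = 27 months, with visits at 3, 6, 9, 15, 21 and 27 months after the qualifying visit. Fluoxetine: 30 − 6 = 24 months, with visits at 3, 6, 12, 18 and 24. The two sets of times coincide only at 3 and 6.

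**The case against.** The strongest reply is that the phrase is plainly a slip and that the numerals themselves may be wrong. If months 3 and 6 were meant, fluoxetine remissions at month 6 would be admitted. Study visits, Table 2 and the Figure 3 legend make that plausible. This stands, and it is why the finding is limited to readings that keep the printed months. A reader might infer that every conceivable reading fails; the documents do not support that. But changing the months is a new definition, which someone has to write. Even then, combination after fluoxetine, which starts at month 6, would need its own rule.

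A reader might also infer that months 3 to 6 are counted as relapse follow-up while fluoxetine participants are still on treatment. No section says so. Study visits describes continued assessments for remitters at months 9 and 12 onward, and Table 2 counts month 6 for IPT only. The inference holds only if follow-up begins at the qualifying visit.

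Nor would everyone who receives combination be absent from the set. A participant who remitted early, lost remission and was then re-randomised could be in it, but through the first-line remission.

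Finally, the SAP may be meant to cover only first-line and re-randomised outcomes. That would explain its silence. It would not supply the missing definition.

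**Conclusion.** The point holds and should be fixed. On every reading that keeps the printed months, the stated set leaves out fluoxetine remissions first seen at month 6 and admits no remission on combination. It therefore cannot test Hypothesis 1b as worded, and it conflicts with Table 2, row 3. The Abstract and Sample size calculations also disagree with the hypothesis on whether combination belongs in the relapse comparison.

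This rests on the treatment calendar and the re-randomisation rule in the documents, not on any assumed rate. The number left out, and the size and direction of any bias, cannot be calculated; a claim that the comparison is biased toward one arm would go beyond the text. It would also go too far to say that no set has been specified. One has, but it is ambiguous and does not fit the hypothesis.

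**What to change.** 1. Replace the set in the Data analysis plan with participants in remission at the end of the first-line course (month 3 for IPT, month 6 for fluoxetine, as in Table 2, row 3). Start relapse follow-up at that visit.
2. Reconcile the Abstract, Hypothesis 1b, the Data analysis plan, Table 2 and Sample size calculations on combination. One option is to add remitters at the first scheduled assessment at or after the end of second-line treatment, state how remitters after a switch are classified, and show first-line and second-line remitters separately. The other is to restrict Hypothesis 1b to first-line remitters.
3. Keep the weighted GEE. As a new proposal, adjust for demographics and baseline BDI and PCL, which the Data analysis plan lists for Hypothesis 1a only. State that remitter groups are not randomised groups and that adjustment does not remove this selection.
4. Reconcile Hypothesis 1a, which the Data analysis plan analyses at month 3 as the end of treatment for both arms, with the month-6 end of fluoxetine. State whether both arms are assessed at month 1.5.
5. Reconcile the two schedules on month 9: Study visits, Clinical evaluators and the Figure 3 legend include it, but Assessment schedule and rationale goes from month 6 to six-month intervals.
6. Add the analysis to the SAP.

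The cost is mainly protocol and SAP wording. If second-line remitters are added, the end of second-line treatment must be stated unless Figure 3, which is not reproduced in the text, already gives it. The downside is unequal follow-up: 27 months after first-line IPT, 24 after first-line fluoxetine, and less after second-line treatment. Visits also fall at different times since remission in the two arms, so the form of time in the model must be specified.
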